5.4. Subject Disposition

Subject disposition will be listed and summarized by group and combined. The following summaries will be provided:

- The total number of screened patients
- The total number of patients in each analysis set
- The total number of patients who discontinued the study treatment and the reasons for the treatment discontinuation
- The total number of patients who discontinued the study, and the reasons for the study discontinuation

Listing of patient disposition will include dates of the first and the last cemiplimab administration, date of the end of treatment, date of end of study, and reasons for treatment and study discontinuation.

5.5. Protocol Deviations

Protocol deviations will be recorded in separate protocol deviation definition document which includes a listing of all patients with protocol deviations and the reason of deviation. The major protocol deviation, such as violation of inclusion/exclusion criteria; post-enrollment deviations which will impact assessment of efficacy or safety endpoints, will be determined before database lock and be summarized by group and combined.

5.6. Measurement of Compliance

Compliance with cemiplimab treatment will be calculated as follows:

$$\text{Treatment Compliance} = \frac{\text{(Number of doses of cemiplimab administered during treatment period)}}{\text{(Number of doses of cemiplimab planned to be administered during period)}} \times 100\%$$

where temporary dose discontinuation is ignored.

The percentage of subjects who have <60%, 60-80%, 80-100%, and >100% compliance will be summarized for each group and combined.

5.7. Exposure to Investigational Product

Exposure to cemiplimab will be examined for each subject and the following variables will be summarized by group and combined:

- The total number of cemiplimab doses administered
- The total dosage of cemiplimab administered (mg)
- Duration of treatment exposure (in weeks) calculated as the minimum of
 1. [date of last dose – date of first dose + 21 days based on Q3 weekly dosing schedule] / 7
or
 2. [date of clinical data cut-off or date of death – date of first dose + 1] / 7
- The number and percentage of patients exposed to cemiplimab will be presented by specific time points of interest (e.g., weeks 6, 12, 18, 24, 36, 72, 108) for each group and combined. The actual dose intensity (mg/week) = total dose received (mg) / duration of treatment exposure (week)
- The relative dose intensity = actual dose intensity / planned dose intensity,
 - Planned dose intensity (mg/week) = planned dose (350 mg) / 3

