10.4.5.3. Treatment Exposure

Duration of exposure, number of dose administered, and dose intensity will be summarized by group. Dose intensity will be calculated by dividing actual dose by body weight.

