8. INTERIM ANALYSIS

An interim analysis of Group 1 patients will be performed at the time of the primary analysis for Group 2. All Group 1 patients enrolled on or prior to the cutoff date will be included in the safety analysis. In order to describe ORR and DOR, Group 1 patients who have the opportunity to be followed from onset of response for at least 6 months will be included in the efficacy analysis. Because responses may emerge slowly in BCC patients (Falchook 2016), and the primary endpoint results are not known prior to data cut, the convention in this study will be that all patients will have the opportunity for at least 6 months to develop response. Given the tumor assessment schedule (every 9 weeks from cycle 1 to 5, and every 12 weeks from cycle 6 to 9), the interim analysis for Group 1 will only include Group 1 patients who have the opportunity to be followed for approximately 57 weeks, including 27 weeks (cycles 1 to 3) for response, plus an additional 30 weeks (cycles 4 to 6) for DOR. If the last patient(s) has early EOS, the timing of data cut will be determined by the enrollment date of the last enrolled patient who remains on study (first dose + approximately 57 weeks).

For regions where alpha spending is not required: For this planned interim analysis on Group 1 patients, the ORR and associated 95% confidence interval will be summarized. As the primary objective of this interim analysis is point estimation on ORR and characterizing the precision of point estimation, there is no hypothesis testing associated with this interim analysis. Also, no decisions will be made regarding study conduct associated with the interim analysis. Therefore, Type I error adjustment is not applicable for this planned interim analysis. At the time of the final analysis for Group 1 patients, 95% exact confidence intervals will be reported.

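### SAP 5.7 divides the full dose received by an exposure time cut at data cut-off or death, which inflates relative dose intensity for patients last dosed fewer than 20 days earlier

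*SAP*

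**What the plan says.** SAP 5.7 gives a "Duration of treatment exposure (in weeks) calculated as the minimum of" two quantities. The first is "date of last dose – date of first dose + 21 days based on Q3 weekly dosing schedule] / 7", which credits the last dose with its full 3-week interval. The second is "date of clinical data cut-off or date of death – date of first dose + 1] / 7", which stops the clock at cut-off or death.

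The same section then uses this duration as a denominator: "The actual dose intensity (mg/week) = total dose received (mg) / duration of treatment exposure (week". It sets "Planned dose intensity (mg/week) = planned dose (350 mg) / 3" and "The relative dose intensity = actual dose intensity / planned dose intensity". Nothing in the section pro-rates the last dose, caps the ratio or excludes short exposures.

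SAP 8 places no follow-up minimum on safety at the Group 1 interim: "All Group 1 patients enrolled on or prior to the cutoff date will be included in the safety analysis". The roughly 57-week requirement there applies to efficacy only.

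Protocol 10.4.5.3 has a different definition: "Dose intensity will be calculated by dividing actual dose by body weight". SAP 1.2.4, which lists departures from the protocol's statistical section, names only three added response endpoints and does not mention dose intensity.

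**The concern.** Relative dose intensity should equal 100% for a patient who receives every planned dose on the planned day, and fall below it when doses are late. That requires each dose in the numerator to be matched by its own interval in the denominator. The first expression in SAP 5.7 does this. The second removes up to 20 days of the last interval and leaves the last dose whole.

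For a patient on or behind schedule the error can only be upward. It arises when the patient is still on drug at the cut or dies soon after a dose. It also matters for delays, because the compliance measure in SAP 5.6 disregards temporary discontinuation. Of the two planned adherence ratios, only relative dose intensity responds to delays between doses.

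At stake is the accuracy of the exposure tables that readers use to interpret safety and efficacy. The body-weight definition in the protocol adds a second problem: it has no time dimension, it does not suit a flat dose, and it gives a different quantity from the SAP's.

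**Working it through.** **Inputs.** Dose 350 mg every 3 weeks, the two exposure expressions, and planned intensity 350/3 = 116.67 mg/week (all SAP 5.7). Minimum opportunity for follow-up of the last patient at the primary cut is about 57 weeks (SAP 5). Planned treatment is 93 weeks, or 5 × 3 + 4 × 4 = 31 doses (Protocol Tables 4 and 5). The documents state no dose-intensity result to reproduce.

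**On-schedule patient.** Let n be the number of doses and d the days from last dose to cut-off or death. In days, the first expression is 21(n−1) + 21 = 21n and the second is 21(n−1) + d + 1. The second is smaller when d is 0 to 19, and the two are equal at d = 20. So for d = 0 to 20

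RDI = [350n ÷ ((21(n−1)+d+1)/7)] ÷ (350/3) = 21n / (21(n−1)+d+1).

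For d ≥ 20 the first expression applies and RDI = 21n/21n = 100%.

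| Doses n | Maximum (d = 0) | Mean over d = 0 to 20, each equally likely |
|---|---|---|
| 1 | 21/1 = 2100% | 364.5% (median 21/11 = 190.9%) |
| 2 | 42/22 = 190.9% | 136.3% |
| 3 | 63/43 = 146.5% | 120.5% |
| 10 | 210/190 = 110.5% | 105.1% |
| 19 | 399/379 = 105.3% | 102.6% |
| 20 | 420/400 = 105.0% | 102.5% |
| 31 | 651/631 = 103.2% | 101.6% |

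An on-schedule patient with 19 doses is between study days 379 and 399, that is, up to exactly 57 weeks.

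**Delayed patient.** With a total delay of D days between doses and d from 0 to 20, the SAP gives 21n / (21(n−1)+D+d+1). The matched denominator gives 21n / (21n+D). The delay is fully hidden (score of 100% or more) when D + d ≤ 20, so the longest delay that can disappear is 20 days.

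| n | D | d | SAP 5.7 | Matched denominator |
|---|---|---|---|---|
| 2 | 20 | 0 | 42/42 = 100.0% | 42/62 = 67.7% |
| 4 | 20 | 0 | 84/84 = 100.0% | 84/104 = 80.8% |
| 4 | 14 | 0 | 84/78 = 107.7% | 84/98 = 85.7% |
| 20 | 20 | 0 | 420/420 = 100.0% | 420/440 = 95.5% |
| 20 | 42 | 0 | 420/442 = 95.0% | 420/462 = 90.9% |
| 20 | 20 | 20 | 420/440 = 95.5% | 420/440 = 95.5% |

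The 42-day delay stays visible but is understated. Once d reaches 20 the two columns agree.

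**Check of the remedies.** Using the first expression alone gives 21n/21n = 100% for every on-schedule patient. Keeping the truncation but counting the last dose as 350 × (d+1)/21 gives total dose (350/21) × (21(n−1)+d+1). Divided by (21(n−1)+d+1)/7 weeks, this is 350/3 mg/week, again exactly 100%.

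**The case against.** The strongest reply is that this is small where it counts. Dose intensity is descriptive, and no test, decision rule or analysis set depends on it. An on-schedule patient still on drug at the Group 2 primary cut has had about 19 or more doses, so the excess is a few points. Patients who stopped earlier for progression, toxicity, complete response or completion score exactly 100%. Number of doses, total milligrams and duration are tabulated separately, and SAP 5 also reports medians and quartiles, which one outlier barely moves. All of this stands and sets the size of the point.

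Three stronger readings are tempting, and the documents do not support them.

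- A reader might infer that on-schedule patients in general exceed 100%. Only those cut fewer than 20 days after their last dose do.
- A reader might take 2100% as typical, or note that one such patient among 53 gives a mean of (52 × 100 + 2100)/53 = 137.7%. This needs a single dose given on the day of cut-off or death, with everyone else at exactly 100%. The documents do not say that Group 1 will still be enrolling at the interim, and Protocol 10.2 provides for closing it early if accrual is poor. Early death is possible, but eligibility requires an anticipated life expectancy above 12 weeks.
- A reader might infer that delays are masked throughout. Full masking stops at 20 days in total, and only affected patients are involved.

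It can also be objected that the untruncated denominator credits time after death or beyond the cut. It does, by up to 20 days, but only to match a dose already counted in full. The remedy is also incomplete: a patient on hold and last dosed 60 days before the cut scores 100% under either rule if earlier doses were on time.

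**Conclusion.** The point holds, with limited reach. As written, SAP 5.7 overstates relative dose intensity for patients whose cut-off or death falls fewer than 20 days after the last dose, and for no one else. For an on-schedule patient at about 57 weeks the excess averages about 2.6 points, with a maximum of 5.3. It is substantial only after very few doses, which can arise through early death or in the Group 1 interim safety set. Delays in affected patients are understated, and those totalling up to 20 days can be hidden. The ORR analysis is not affected.

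The figures assume full 350 mg doses, first-course treatment, exact 21-day spacing apart from the stated delay, and, for the means, a cut equally likely on each day of the interval. Dosing early within the ±3-day visit window can also give slightly more than 100%, legitimately.

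The protocol's body-weight definition is a separate and plain conflict with the SAP. Protocol section 10 is only the basis for the SAP, so the SAP may differ, but the difference should be recorded.

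**What to change.** In SAP 5.7, keep the minimum rule for duration of exposure. For actual and relative dose intensity, use (date of last dose − date of first dose + 21 days)/7 as the denominator for all patients, without truncation. On-schedule first-course patients then score exactly 100%, and delays between doses show in full. Pro-rating the last dose over the truncated interval is equivalent for on-schedule patients. Neither change reveals a hold still ongoing at cut-off, which the current rule also misses.

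Separately, replace the body-weight sentence in Protocol 10.4.5.3 with the SAP's mg/week definition, or list the change in SAP 1.2.4.

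The cost is one line of SAP 5.7, one derived variable, and one sentence in the protocol or one entry in SAP 1.2.4. No new data are needed. Reported dose intensity falls for the affected patients, by about 2.6 points on average for those on schedule at about 57 weeks.

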5.8. Analysis of Efficacy Variables

The analysis of efficacy data will be performed based on the FAS. The summary of efficacy results will be presented by group (i.e., Group 1 and Group 2).

The primary efficacy variable will be tested. All other efficacy variables will be summarized descriptively.

5.8.1. Analysis of Primary Efficacy Variable

The ORR according central review will be summarized by group and the corresponding 2-sided 95% exact binomial confidence intervals will be derived using the Clopper-Pearson method (Clopper 1934). BOR will also be summarized.

The primary analysis of efficacy is based on the exact binomial confidence interval approach of ORR. If the lower limit of 2-sided 95% exact binomial confidence interval of observed ORRs excludes 15% for Group 1 or excludes 20% for group 2, the study treatment is deemed effective

for that group, respectively. For regions requiring alpha spending, details are provided in Section 8 for alpha adjustment due to interim analysis for Group 1.

5.8.2. Analysis of Secondary Efficacy Variables

ORR derived from the overall response that is based on investigator review will be analyzed similarly as primary efficacy variable.

DOR: The distribution of DOR will be estimated using the Kaplan-Meier method. The median DOR along with its 95% CI will be presented by group and Kaplan-Meier estimates with 2-sided 95% CIs at specific time points (for example, 6, 12, 18 and 24 months) will be summarized. The Kaplan-Meier curves will be displayed by group. DOR will also be summarized descriptively by range. Number and percentage of patients with DOR at specific time periods of interest (e.g., $>=3$ months, $>=6$ months, $>=12$ months, $>=18$ months, etc.) will be summarized by group.

PFS: The distribution of PFS will be estimated using the Kaplan-Meier method. The median PFS along with its 95% CI will be presented by group and Kaplan-Meier estimates with 2-sided 95% CIs at specific time points (for example, 6, 12, 18 and 24 months) will be summarized. The Kaplan-Meier curves will be displayed by group.

OS: The distribution of OS will be estimated using the Kaplan-Meier method. The median OS along with its 95% CI will be presented by group and Kaplan-Meier estimates with 2-sided 95% CIs at specific time points (for example, 6, 12, 18 and 24 months) will be summarized. The Kaplan-Meier curves will be displayed by group. A variant of OS defined by censoring patients at the start date of subsequent therapy will be summarized and displayed by Kaplan-Meier approach as a sensitivity analysis.

TTR will be summarized descriptively by group and at specific time periods of interest (e.g., <2 months, 2 to 4- months, 4 to 6- months, $>=6$ months).

CR rate, DCR and dDCR will be summarized by group and the corresponding 2-sided 95% exact binomial confidence intervals will be derived using the Clopper-Pearson method.

The duration of response and the best percentage change from baseline in target lesions will be presented by swimmer plot and waterfall plot respectively.

5.8.3. Analysis of Quality of Life Variables

Subject disposition rates:

The subject disposition by group for all patient-reported outcomes (PRO) assessment timepoints will be provided:

- The number of subjects with PRO assessment expected; a PRO assessment is expected as long as the subject is alive and on treatment
- The number and % of subjects with PRO assessment not expected due to progression

- The number and % of subjects with PRO assessment not expected due to death
- The number and % of subjects with PRO assessment not expected due to other reasons

The subject disposition by treatment group by PRO assessment timepoint will also be provided graphically.

PRO completion rates:

PRO instrument completion rate at each PRO assessment timepoint will be reported for the EORTC QLQ-C30 (Physical function, role function, and global health status) and Skindex-16 (Emotions, Symptoms, and Functioning). Completion rate will be calculated among subjects who are expected to have PRO assessments. The following will be provided:

- The number and % of subjects meeting at least the minimum requirements for scoring of the instrument; these requirements are as follows:
- EORTC QLQ C30: at least one subscale can be calculated
- Skindex-16: at least one domain can be calculated

The completion rates by treatment group at each PRO assessment timepoint will also be provided graphically.

Descriptive analyses:

The quality of life of patients will be repeatedly measured by the EORTC QLQ-C30 and Skindex-16 at the day 1 of each treatment cycle and end of treatment visit. The change scores of each component of QLQ-C30 and Skindex-16 will be summarized descriptively at each post-baseline time point. The summary scores of each component of QLQ-C30 and Skindex-16 will also be graphically depicted by longitudinal plots. Partial missing data in QLQ-C30 and Skindex-16 will be addressed by the scoring algorithm, no additional imputations will be conducted for missing data.

Additional analysis of PROs will be performed and the details will be included in a separate PRO SAP.

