8. STUDY SCHEDULE OF EVENTS AND PROCEDURES

8.1. Schedule of Events

Study assessments and procedures in the treatment periods are presented in [Table 4](#) and [Table 5](#). Study assessments and procedures in the follow-up period are presented in [Table 6](#). Study visits can be scheduled so as not to fall on weekends or holidays, after discussion and approval by the Sponsor.

Table 4: Schedule of Events for Treatment Cycles 1 - 5 (9-Week Cycles)

Study Procedure	Screening	Cycle 1				Cycles 2-5 ¹				End of Study
		1	22±3	43±3	64±3	1 ²	22±3	43±3	64±3	
Visit Days	-28 to -1									30 days after last dose cemiplimab ³
Clinical Assessments and Study Treatment										
Informed Consent ⁴	X ⁴									
[REDACTED]	X									
Medical/Oncology History	X									
Complete Physical Examination, Neurological Exam, and ECOG PS ⁵	X	X				X				X
Physical Examination (Limited) ⁶			X	X			X	X		
12-Lead ECG ⁷	X	X				X				X
Vital Signs and Weight ⁸	X	X	X	X		X	X	X		X
Height	X									
Brain MRI ⁹	X									
350 mg cemiplimab Q3W IV		X	X	X		X	X	X		
Laboratory Tests										
Hematology ¹⁰ and Blood Chemistry ¹¹	X	X	X	X		X	X	X		X
Serum HCG ≤72 Hour Predose ¹²	X									
Urine Pregnancy Test										X ¹³
Urinalysis ¹⁴	X	X				X				X
aPTT; INR		X								X
HBV, HCV, HIV	X									
Immune Safety and PK Blood Samples										
RF and ANA		X				X				X
TSH and CRP		X				X				X
ADA ¹⁵		X ¹⁵		X		X ¹⁵				X
Cemiplimab PK/Drug Conc ¹⁶		X	X	X		X				X
Pathology and Exploratory Biomarker Research Samples										
Archived tissue for histological confirmation of BCC ¹⁷	X									
Tumor biopsies for Group 2 ¹⁸	X		X							
[REDACTED]		X								

Study Procedure	Screening	Cycle 1				Cycles 2-5 ¹				End of Study
Visit Days	-28 to -1	1	22± 3	43± 3	64±3	1 ²	22±3	43±3	64±3	30 days after last dose cemiplimab ³
Response Imaging and Other Assessments										
CT/MRI and/or digital photography ¹⁹	X		X ²⁰		X				X	X
EORTC QLQ-C30, Skindex-16 ²¹		X				X				X
Concomitant medications ²²	X	X	X	X	X	X	X	X	X	X
Adverse Events ²³	← continuous monitoring→									

8.1.1. Footnotes for the Schedule of Events for Treatment Cycles 1 – 5 (9-Week Cycles) – Table 4

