ADA=anti-drug antibody; AE=adverse event; ANA=antinuclear antibody; ECOG PS=Eastern Cooperative Oncology Group Performance Status; EOS=end of study; HBV=hepatitis B virus; HCG=human chorionic gonadotropin; HCV=hepatitis C virus; HIV=human immunodeficiency virus; INR=International Normalized Ratio; MRI=magnetic resonance imaging; RF= rheumatoid factor; TSH=thyroid-stimulating hormone

1. There are 5 treatment cycles of 9 weeks in this table, followed by 4 treatment cycles of 12 weeks in the subsequent table. The maximum number of treatment cycles is 9 (planned 93 weeks total).

2. Should occur at least 59 days from day 1 of previous cycle, and no sooner than 18 days after the previous dose.

(1) The EOS visit is for patients who experience PD requiring study discontinuation in cycles 1 through 5. This visit should occur 30 days (allowed window: 21 to 42 days) after the last dose of cemiplimab. The only posttreatment assessment that can occur outside of this timeframe is the posttreatment biopsy (required in Group 2) that can be obtained at any time within 28 days of last dose of cemiplimab.

(2) Patients who complete the required events in Table 4 and Table 5 (excluding the EOS visit) with any status other than PD (eg, CR, PR, or SD) will go on to complete the assessments for follow up in Table 6.

3. Patients who do not experience PD do not need to complete the EOS visit at end of cycle 9. Patients will be followed quarterly for survival and tumor treatment status, if available.

4. Informed consent must be provided before the initiation of screening procedures, and must be obtained within 45 days prior to cycle 1/day 1. All screening assessments must be performed within 28 days prior to cycle 1/day 1 (with exception for brain MRI according to footnote 9, as per below). Assessments performed as part of standard of care that fall within the screening window but before informed consent is obtained may be used for screening, and need not be repeated for enrollment eligibility.

5. Complete physical examination includes head and neck, lungs, heart, abdomen, lymph nodes, extremities, and skin. A brief neurologic examination should also be performed. The exam may be performed ≤ 72 hours prior to study treatment. Complete physical exam must be accompanied by assessment and documentation of ECOG Performance Status.
6. Limited physical exam includes lungs, heart, abdomen, and skin.

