Immune Safety and PK Blood Samples						
RF and ANA	X					X
TSH and CRP	X					X
ADA ¹⁰	X					X
Cemiplimab PK/Drug Conc ¹¹	X					X
Response Imaging and Other Assessments						
CT/MRI and/or digital photography ^{12,13}					X	X
EORTC QLQ-C30, Skindex-16 ¹⁴	X					X
Concomitant medications ¹⁵	X	X	X	X	X	X
Adverse Events ¹⁶	← continuous monitoring→					

8.1.2. Footnotes for the Schedule of Events for Treatment Cycles 6 – 9 (12-Week Cycles) – Table 5

ADA=anti-drug antibody; AE=adverse event; ANA=antinuclear antibody; ECOG PS=Eastern Cooperative Oncology Group Performance Status; EOS=end of study; HBV=hepatitis B virus; HCG=human chorionic gonadotropin; HCV=hepatitis C virus; HIV=human immunodeficiency virus; INR=International Normalized Ratio; MRI=magnetic resonance imaging; RF= rheumatoid factor; TSH=thyroid-stimulating hormone

1. Should occur at least 59 days from the previous day 1 of cycle 5 (for cycle 6), or 81 days from day 1 of previous cycle (for cycles 7 – 9), and no sooner than 18 days after the previous dose.
 - (1) The EOS visit is for patients who experience PD requiring study discontinuation in cycles 6 through 9. This visit should occur 30 days (allowed window: 21 to 42 days) after the last dose of cemiplimab. The only posttreatment assessment that can occur outside of this timeframe is the post treatment biopsy (required in Group 2) that can be obtained at any time within 28 days of last dose of cemiplimab.
 - (2) Patients who complete the required events in [Table 4](#) and [Table 5](#) (excluding the EOS visit) with any status other than PD (eg, CR, PR, or SD) will go on to complete the assessments for follow up in [Table 6](#).
2. Patients who do not experience PD do not need to complete the EOS visit at end of cycle 9. Patients will be followed quarterly for survival and tumor treatment status, if available
3. Complete physical examination includes head and neck, lungs, heart, abdomen, lymph nodes, extremities, and skin. A brief neurologic examination should also be performed. The exam may be performed ≤ 72 hours prior to study treatment. Complete physical exam must be accompanied by assessment and documentation of ECOG Performance Status.
4. Limited physical exam includes lungs, heart, abdomen, and skin.

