10.4.4.2. Quality of Life and Skindex-16 Analysis

The patient-reported outcomes and quality of life of patients will be repeatedly measured by the EORTC QLQ-C30 and the Skindex-16 at day 1 of each treatment cycle. The change scores of the

QLQ-C30 and the Skindex-16 will be summarized descriptively at each post-baseline time point. The summary scores of the QLQ-C30 and the Skindex-16 will also be graphically depicted by longitudinal plots.

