CR rate is determined by the proportion of patients with best overall response of CR (tumor biopsy confirmation is required for Group 2 patients).

Disease control rate (DCR) is determined by the proportion of patients with BOR of CR, PR, or SD.

Durable disease control rate (dDCR) is defined as the proportion of patients best overall response of CR, PR, or SD without progression for at least 27 weeks (allowing tumor assessment made 1 week earlier than week 27).

Patient-reported quality of life are measured by the EORTC QLQ-C30 (Aronson 1993) and Skindex-16 (Chren 2001) on day 1 of every cycle and at EOT.

- The global health status/QoL, five functional scales (physical, role, cognitive, emotional and social), and three symptom scales (fatigue, pain, nausea and vomiting) and a number of single items assessing additional symptom commonly reported by cancer patients (dyspnoea, loss of appetite, insomnia, constipation and diarrhoea) and perceived financial impact of the disease will be computed using the QLQ-C30 scoring procedures (Fayers 2001).
- The scores for global and three domains of symptoms (4 items), functioning (5 items), and emotions (7 items) will be computed using the Skindex-16 scoring procedures (Chren 2001).
- Change scores are defined as change of summary score of EORTC QLQ-C30 or Skindex-16 from day 1 of first treatment cycle.

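### The SAP analyses quality of life at an end-of-treatment visit that the protocol does not schedule; the nearest visit is scheduled for patients with PD, so the summary is selected on progression and its completion denominator is unclear

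*SAP*

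**What the plan says.** **SAP.** Section 4.4.2 has the QLQ-C30 and Skindex-16 completed "on day 1 of every cycle and at EOT". Section 5.8.3 says they are "repeatedly measured by the EORTC QLQ-C30 and Skindex-16 at the day 1 of each treatment cycle and end of treatment visit". Change scores are to be summarised at each post-baseline time point, and a completion rate reported at each assessment time point among patients from whom a form is expected. The rule for that is "a PRO assessment is expected as long as the subject is alive and on treatment". Patients not expected are counted by reason: progression, death or other.

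**Protocol, analysis section.** Section 10.4.4.2 plans the QLQ-C30 and "Skindex-16 at day 1 of each treatment cycle" and names no later time point. SAP 1.2.4 lists TTR, DCR and dDCR as its only departures from the protocol's statistical section.

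**Protocol, schedule.** In Tables 4 and 5 the row "EORTC QLQ-C30, Skindex-16" is marked on day 1 of the cycles and in the End of Study column. Neither table has an end-of-treatment column. On who attends EOS, the Table 4 footnotes say "The EOS visit is for patients who experience PD requiring study discontinuation in cycles 1 through 5", and the Table 5 footnotes say "The EOS visit is for patients who experience PD requiring study discontinuation in cycles 6 through 9". Both sets add: "Patients who do not experience PD do not need to complete the EOS visit at end of cycle 9". Section 8.1.4 sends patients who stop for reasons other than PD, such as toxicity or confirmed CR, to the Table 6 schedule, which has no questionnaire row.

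**The concern.** EOT is not defined in either document. The only post-treatment visit at which the questionnaires are scheduled is EOS, and the footnotes tie that visit to progression. A change score labelled end of treatment would then be selected on outcome. Patients who finish nine cycles without PD, stop after confirmed CR or stop for toxicity have no form scheduled at that point. Nothing in SAP 5.8.3 tells the reader that the time point covers a different population from the cycle day 1 series.

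The completion rule adds a second problem. The patients scheduled to fill in the EOS form are off treatment and have progressed, so the rule classes them as not expected. The table meant to show how complete the data are does not work at the visit where selection is strongest.

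Quality of life is a named secondary objective, and in this SAP its analysis is description only. A summary with an unclear population is the main way that such an analysis can mislead.

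**Working it through.** The documents give no sample-size, power or alpha figure on this point. The check sets the passages side by side, with simple calendar arithmetic.

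**1. Calendar.** Five 9-week cycles and four 12-week cycles give 5 × 9 + 4 × 12 = 93 weeks, which reproduces the protocol's treatment length. Cycle 9 day 1 falls 5 × 9 + 3 × 12 = 81 weeks after first dose. The last planned dose, on day 64 of cycle 9, falls at 81 + 9 = 90 weeks. A completer without PD therefore has no form scheduled after week 81, so none for the last 93 − 81 = 12 weeks of the treatment period and none after it.

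**2. Who has a post-treatment form scheduled.**

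| Patient | Next schedule | Questionnaire there? |
|---|---|---|
| Stops for PD in cycles 1 to 9 | EOS, 30 days (footnote window 21 to 42) after last dose | Yes |
| Completes nine cycles without PD | Table 6 | No |
| Stops for toxicity or confirmed CR | Table 6 | No |
| Progresses during follow-up | A follow-up visit is handled as EOS (Table 6, footnote 10) | Yes, but later after the last dose |

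Every row with a form is a progressor. The last row also means that EOS forms come at mixed times since treatment.

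**3. Completion denominator at that visit.** There are two possible readings of being on treatment.
- *Literal.* At 21 to 42 days after the last dose, with treatment stopped for PD, nobody is on treatment. Expected = 0, and the rate is undefined whatever number of forms arrives.
- *Borrowed from SAP 5.9.1.* The adverse-event on-treatment period runs to 105 days after the last dose (ending earlier if new systemic anticancer therapy or retreatment starts). EOS at 21 to 42 days would normally fall inside it. The denominator would then also count living patients who left treatment without PD and have no form scheduled, so completion could not exceed roughly the progressors' share.

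Neither reading gives a rate that shows how many scheduled forms were returned.

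**4. Possible size (illustration).** The documents give no progression rate. Assume that a share p of patients progress, with p from 30% to 70%. The number with an EOS form scheduled is then at most N × p:
- Group 1 (N = 53): 53 × 0.30 ≈ 16 to 53 × 0.70 ≈ 37.
- Group 2 (N = 84): 84 × 0.30 ≈ 25 to 84 × 0.70 ≈ 59.

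If non-progressors scored d points better than progressors, the progressors' mean would differ from the all-patient mean by (1 − p) × d. With d = 10, also an assumption, that is 0.7 × 10 = 7 points at p = 30% and 0.3 × 10 = 3 points at p = 70%.

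**The case against.** The strongest reply is that the documents are looser than a strict PD-only reading.

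- **Non-PD patients are excused from EOS, not barred.** The EOS column itself is headed only by time since last dose. Footnotes 15 and 16 to Table 4, and 10 and 11 to Table 5, place end-of-study or 30-day samples on patients described without reference to PD. Section 6.3 refers prematurely withdrawn patients to Section 8.1.4 without saying which of its routes applies. This stands in part. Those footnotes concern ADA and PK blood samples, not questionnaires, but a reader who infers that no patient without PD can contribute a form goes too far.
- **The 105-day period may be what the SAP means by on treatment.** SAP 5.8.3 does not define the term, so a zero denominator is the result of the literal reading and not a certainty. But the 105-day period is defined for adverse events and is not cited for PROs, and step 3 of the working shows that borrowing it gives a different unsuitable denominator.
- **The disposition counts already show absence.** They do, by reason and at each time point, so the selection is not wholly hidden. They do not separate patients who had no form scheduled from patients who missed one.
- **The SAP does not say that EOT is plotted as the group's last point.** Correct. It promises longitudinal plots without saying how this visit appears, so that reading is an inference.
- **A separate PRO SAP is planned.** It covers additional analyses; the completion and change-score summaries at issue are specified in this SAP.
- **A last on-treatment form at week 81 is a scheduling choice.** Agreed; it is not itself an error.

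**Conclusion.** The point holds in a limited form. The SAP names a quality-of-life time point that the protocol does not schedule and that SAP 1.2.4 does not declare as a change. If EOT means the EOS visit, the only candidate, the change score there describes essentially progressors as scheduled, and the completion rule either leaves the denominator empty or fills it with patients who had no form due.

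A reader might infer that the trial's quality-of-life result as a whole, or its efficacy result, is compromised. The documents do not support that. Quality of life is descriptive with no hypothesis test, the cycle day 1 series planned in protocol 10.4.4.2 is unaffected, and ORR does not depend on it.

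The size cannot be fixed from the documents. The 3 to 7 point range rests entirely on an assumed progression share of 30% to 70% and an assumed 10-point difference. The structural finding needs neither assumption. This should be corrected, but it is not critical to the trial's conclusions.

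**What to change.** In SAP 4.4.2 and 5.8.3:

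1. Replace the EOT wording with: EOS visit (scheduled for patients with PD). If the sponsor meant another visit, say which one and who attends it.
2. Summarise that visit separately from the cycle day 1 series, and do not present it as the group's end-of-treatment value.
3. For that visit, define a form as expected when the patient is alive and due an EOS visit under the protocol.
4. Beside the completion rate, report the number of patients off treatment without PD for whom no questionnaire was scheduled. Item 3 alone could give a high completion rate among progressors and still hide the selection; this count makes it visible.

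This costs SAP wording and one extra count, with no new data. The downside is that no whole-group end-of-treatment figure can be reported.

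Optional: if such a figure is wanted, add both questionnaires at Follow-up 1 in Table 6. That visit already exists, but the addition needs a protocol amendment and two more forms per patient. It would still not cover everyone, because patients who withdraw consent or die before the visit remain absent.
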